**Instructions to subject:**

- Dose investigational product as instructed
- [REDACTED]
- [REDACTED]
- Return for Visit 3 scheduled on Day 8 ± 1 day.

**5.1.3. Visit 3: Day 8 ± 1 day – Diary Collection Visit**

This visit will occur on Day 8 ± 1 day as calculated from Visit 2: Day 1, and the following evaluations will be performed:

- Use of any concomitant medications since the last visit
- Occurrence of any AEs since the last visit
- [REDACTED]
- Subject-rated assessment of ocular discomfort

**Instructions to subject:**

- Dose investigational product as instructed
- [REDACTED]
- [REDACTED]
- Return for Visit 4 scheduled on Day 15 ± 1 day.

**5.1.4. Visit 4: Day 15 ± 1 day – Study Visit**

This visit will occur on Day 15 ± 1 day as calculated from Visit 2: Day 1, and the following evaluations will be performed/assessed:

- Use of any concomitant medications since the last visit
- Occurrence of any AEs since the last visit
- [REDACTED]
- Used and unused double-masked investigational product collected, counted, and compliance assessed (via subject diary)
- Subject-rated assessment of ocular discomfort

- Investigator-rated assessment of bulbar conjunctival hyperemia
- [REDACTED]
- BCVA
- Slit Lamp Biomicroscopy:
- Corneal fluorescein staining
- Lissamine Green conjunctival staining
- IOP measurement
- Subject will receive a re-supply of double-masked investigational product to last until Visit 6.

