**Table 2: COMPOSITION OF KPI-121 0.25% (w/v) DRUG PRODUCT**

**Table 3: COMPOSITION OF VEHICLE**

At Visit 1, eligible subjects will receive 2 bottles of single-masked, investigational product (vehicle) from a common site level supply. The bottle labels for the single-masked period contain the following information: sponsor name, protocol number, lot number, storage temperature, and required statement(s) per the appropriate regulatory agency.

The randomized, double-masked, investigational product kit consists of a box that contains 3 dropper bottles of investigational product. At Visit 2 (Day 1/Randomization), subjects will receive 2 bottles of double-masked investigational product (KPI-121 0.25% ophthalmic suspension or vehicle) from their assigned kit. At Visit 4 (Day 15 ± 1 day), subjects will receive 1 additional bottle of investigational product from their assigned kit. All bottles will

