**5.1.2. Visit 2: Day 1 (Randomization)**

The randomization visit will occur  $14 \pm 1$  days after Visit 1 (Screening). This visit should be scheduled in the morning (if possible) to allow for administration of QID dosing of investigational product during the day for eligible subjects.

Eligible subjects who continue to meet the eligibility criteria ([Section 4](#)) will continue in the study. The following will be performed/assessed:

- Use of any concomitant medications since the last visit
- Occurrence of any AEs since the last visit
- [REDACTED]
- Used and unused single-masked run-in investigational product collected, counted, and compliance assessed (via subject diary)
- Subject-rated assessment of ocular discomfort
- Investigator-rated assessment of bulbar conjunctival hyperemia
- [REDACTED]
- BCVA
- Slit Lamp Biomicroscopy
- Corneal fluorescein staining
- Lissamine Green conjunctival staining
- IOP measurement
- Upon verification of study eligibility ([Section 4](#)), randomization of appropriate subjects to receive QID dosing of either KPI-121 0.25% ophthalmic suspension or vehicle.

The following will be performed for all randomized subjects:

- Instillation of randomized investigational product
- AE Assessment
- Dispensing of double-masked, investigational product (2 bottles) and instructions for administration
- [REDACTED]

The first dose of double-masked investigational product will be administered in the clinic under the supervision of a designated dosing coordinator. This dosing coordinator, who is not

responsible for study assessments, will also be required to dispense and retrieve investigational product to the subjects. Prior to administration of investigational product, subjects will be instructed regarding proper method for instillation of their assigned investigational product including but not limited to shaking investigational product bottle prior to each instillation. Since subjects will receive 1 dose of investigational product in the clinic, they will self-administer at most 3 additional doses of investigational product on the first day.

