## 6. TREATMENT OF SUBJECTS

### 6.1. INVESTIGATIONAL PRODUCTS TO BE ADMINISTERED

All subjects meeting eligibility criteria at Visit 1 will receive 2 bottles of single-masked investigational product (vehicle). Subjects who continue to meet eligibility criteria at Visit 2 will be randomized to either KPI-121 0.25% ophthalmic suspension or vehicle. One kit of randomized investigational product containing 3 dropper bottles will be allocated to each subject at Visit 2. At Visit 2 (Day 1/Randomization), subjects will receive 2 bottles of double-masked investigational product (KPI-121 0.25% ophthalmic suspension or vehicle). At Visit 4 (Day  $15 \pm 1$  day), subjects will receive 1 additional bottle of double-masked investigational product from the kit allocated. All bottles will be returned to the site at Visit 6 (Day  $29 \pm 1$  day). The investigational product will be stored at the site in a secure area with limited access at controlled room temperature (15-25°C/59-77°F).

Subjects will be asked to administer investigational product QID. Prior to each instillation, subject will be instructed to shake investigational product bottle. The subjects will record the time of administration of each dose of investigational product at the time of instillation ([Appendix 12](#)). Compliance with instillation of investigational product will be reviewed and assessed at each clinic visit.

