### **6.3. INVESTIGATIONAL PRODUCT USE COMPLIANCE**

Compliance will be assessed by comparing investigational product accountability records with the [REDACTED]. The site will document this comparison along with verification of the numbers of used and unused investigational product bottles. The numbers of missed doses as assessed at each clinic visit should be documented in the eCRF.

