**16. APPENDICES**

**CONFIDENTIAL**

APPENDIX 1: SUMMARY OF EVENTS

Procedures	Visit 1	Visit 2	Visit 3	Visit 4	Visit 5	Visit 6
	Screening	Randomization	[REDACTED]	Study Visit	[REDACTED]	End of Study Visit
	14 ± 1 Days Prior to Day 1	Day 1	Day 8 (±1 day)	Day 15 (±1 day)	Day 22 (±1 day)	Day 29 (±1 day)
Informed Consent, HIPAA Authorization and Medical History	X					
Concomitant medication query	X	X	X	X	X	X
UPT a	X					X
Inclusion/Exclusion	X	X				
AE Assessment	X	X	X	X	X	X
Subject-rated assessment of ocular discomfort	X	X	X	X	X	X
[REDACTED]	X	X c	X c	X c	X c	X c
Investigator-rated assessment of bulbar conjunctival hyperemia	X	X		X		X
[REDACTED]		X		X		X
BCVA	X	X		X		X
Slit lamp biomicroscopy	X	X		X		X
Corneal fluorescein staining	X	X		X		X
Lissamine Green conjunctival staining	X	X		X		X
Unanesthetized Schirmer Test Assessment	X					
IOP measurement	X	X		X		X
Dilated ophthalmoscopy	X					X

Procedures	Visit 1	Visit 2	Visit 3	Visit 4	Visit 5	Visit 6
Investigational product administration in-clinic	X b	X				
Dispense investigational product	X b	X		X		
	X b	X	X	X	X	
Collect investigational product		X b				X
		X b	X	X	X	X

aWomen of childbearing potential only; bRun-In Product [REDACTED]

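### Does collecting product at Visit 4 (Section 5.1.4), when all bottles are due back at Visit 6 (Sections 3.5.1 and 6.1), affect the trial's results?

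*Combined protocol and SAP*

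**What the plan says.** Section 5.1.4 includes this among the Visit 4 procedures: "Used and unused double-masked investigational product collected, counted, and compliance assessed (via subject diary". It ends the list with: "Subject will receive a re-supply of double-masked investigational product to last until Visit 6".

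The two supply sections describe a three-bottle kit, with two bottles given at Visit 2. At Visit 4, according to Section 3.5.1 (text after Table 3), "subjects will receive 1 additional bottle of investigational product from their assigned kit". Section 6.1 says the same and adds: "All bottles will be returned to the site at Visit 6". Section 3.5.1 has the same return rule.

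In Appendix 1 the row "Collect investigational product" is marked at Visit 2, with a footnote for run-in product, and at Visit 6. It is blank at Visit 4.

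For the run-in, Section 3.5.1 says that "eligible subjects will receive 2 bottles of single-masked, investigational product (vehicle) from a common site level supply", and Section 5.1.2 closes that period at Visit 2 with "Used and unused single-masked run-in investigational product collected, counted, and compliance assessed (via subject diary". Section 6.3 compares accountability records with a redacted record, asks for "verification of the numbers of used and unused investigational product bottles", and has missed doses entered in the eCRF at each clinic visit.

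**The concern.** Section 5.1.4 uses the same phrase as Section 5.1.2 (end of run-in) and Section 5.1.6 (end of study). At both of those visits the product leaves the subject and Appendix 1 marks a collection. A site could therefore keep the Visit 2 bottles at Visit 4. Fewer than three bottles would then be left to come back at Visit 6, and Appendix 1 would have missed a collection.

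Three consequences would deserve attention if they were real:

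- **Supply.** The subject would have one 5.5 mL bottle for about 14 days, against two for the run-in and two for Days 1 to 15 under the same dosing instruction.
- **Timing.** Visit 4 to Visit 6 contains both co-primary assessments (Section 9.1.2): the diary severity score from Visit 5 to the day before Visit 6, and hyperemia at Visit 6.
- **Compliance data.** Bottle counts under Section 6.3 could mean different things across up to 12 centers.

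**Working it through.** The plan states no figure on this point, so there is nothing to reproduce. The check has three parts.

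**1. The passages side by side**

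| Place | Dispensed at Visit 4 | Visit 2 bottles |
|---|---|---|
| 3.5.1 | 1 additional | All bottles returned at Visit 6 |
| 6.1 | 1 additional | All bottles returned at Visit 6 |
| Appendix 1 | Dispensing marked | No collection marked at Visit 4; marked at Visit 6 |
| 5.1.4 | Re-supply to last until Visit 6 | Collected and counted; onward handling not stated |

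The Appendix 1 blank appears genuine: the neighbouring dispensing row reads correctly at Visits 1, 2 and 4. Three places agree and one bullet differs. That bullet fits the others if the bottles are brought in, counted and handed back. Two subject instructions for Visit 4, two Visit 4 procedure lines and part of the Appendix 1 labels and footnote are redacted, so a hand-back instruction may exist out of sight.

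**2. What the adverse reading would need**

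Inputs: 5.5 mL per bottle (Sections 1.1 and 3.5.1); 1 to 2 drops in each eye four times a day (Synopsis); Visit 4 on Day 15 ± 1 and Visit 6 on Day 29 ± 1, so 28 − 16 = 12 to 30 − 14 = 16 days, nominally 14. Drop volume is not given.

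Drops needed = drops per eye × 2 eyes × 4 doses × days. Largest drop that one bottle can cover = 5500 microlitres / drops needed.

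| Days | 1 drop per eye | Largest drop (microlitres) | 2 drops per eye | Largest drop (microlitres) |
|---|---|---|---|---|
| 12 | 96 | 57.3 | 192 | 28.6 |
| 14 | 112 | 49.1 | 224 | 24.6 |
| 16 | 128 | 43.0 | 256 | 21.5 |

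At an assumed 25 microlitres and 2 drops per eye, the need is 192 × 25 = 4.8 mL over 12 days, 224 × 25 = 5.6 mL over 14 and 256 × 25 = 6.4 mL over 16, against 5.5 mL. At 1 drop per eye over 14 days it is 112 × 25 = 2.8 mL. One bottle is thus enough or not depending on drop number, drop size and visit window. If the Visit 2 bottles stay with the subject, the kit holds 3 × 5.5 = 16.5 mL and covers 2 drops per eye for 28 days (448 drops) with drops up to 16500/448 = 36.8 microlitres.

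**3. Whether any result depends on the answer**

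- *Between arms.* Both arms have the same bottles, kit and dispensing schedule under masking (Sections 3.5.1 and 3.5.2). Nothing ties a site's handling of returned bottles to a subject's allocation.
- *Compliance.* The bullet itself assesses compliance from the diary. Section 6.1 has each dose time recorded at instillation. A whole-bottle count cannot show missed doses.
- *Bottle totals.* Over the study the total is three under either reading: 2 at Visit 4 plus 1 at Visit 6, or 3 at Visit 6.
- *Analysis sets.* The primary analysis is on all randomized subjects (Section 9.1.2), so bottle counts do not decide who is included. The efficacy evaluable definition is left to the SAP and is to be final before unmasking.

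**The case for a change.** The best argument for acting is that the compatible reading is not written down. A site sees the same phrase at three visits, and at two of them it means that the product is taken away. Calling the Visit 4 bottle a re-supply can suggest replacement, whereas the supply sections call it additional. Even if a redacted instruction covers hand-back, Section 5.1.4 and Appendix 1 would still disagree on whether anything is collected at Visit 4. The cure is one line.

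The mismatch stands, and so does the arithmetic. The consequences do not. A shortage requires a site to act against two sections that agree with each other, a subject to use the top of the dosing range, and a drop size that the documents do not give. That the same weeks hold both co-primary time points says when a shortage would fall, not that one occurs. A real shortage would reduce exposure and could cost power, but none is shown, and it would not by itself favour either arm under the null hypothesis. The compliance argument is weak because the diary is the measure and bottle numbers are a cross-check. Checking kit volume against drop volume is a separate supply question, which these documents can neither raise as a fault nor settle.

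**Conclusion.** This is a clerical inconsistency with no demonstrated effect on any estimate, on type I error, on power or on the comparison between arms. No change to the design or statistical analysis follows. The passages on the handling of Visit 2 bottles after the Visit 4 count must be reconciled as routine document housekeeping; no view is taken here on which dispensing or dosing instruction is right.

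The conclusion rests on three things: the consistent supply statements in Sections 3.5.1 and 6.1, which Appendix 1 supports; diary-based compliance; and the absence of any visible analysis that uses bottle counts. It would need another look if the product's drop volume exceeded about 24.6 microlitres (21.5 at the widest visit window), sites had in fact kept the bottles at Visit 4 and subjects used 2 drops per eye, or if the efficacy evaluable population were defined by bottle counts. The documents show none of these.

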**Instructions to subject:**

- Dose investigational product as instructed
- [REDACTED]
- [REDACTED]
- Return for Visit 5 scheduled on Day 22 ± 1 day.

**5.1.5. Visit 5: Day 22 ± 1 day – Diary Collection Visit**

This visit will occur on Day 22 ± 1 day as calculated from Visit 2: Day 1, and the following evaluations will be performed:

- Use of any concomitant medications since the last visit
- Occurrence of any AEs since the last visit
- [REDACTED]
- Subject-rated assessment of ocular discomfort

**Instructions to subject:**

- Dose investigational product as instructed
- [REDACTED]
- [REDACTED]
- Return for Visit 6 scheduled on Day 29 ± 1 day

#### 5.1.6. Visit 6: Day 29 ± 1 day – End of Study Visit

The end-of-investigational-product-use visit will occur on Day 29 ± 1 day as calculated from Visit 2: Day 1, and the following will be performed/assessed:

- Use of any concomitant medications since the last visit
- Occurrence of any AEs since the last visit
- [REDACTED]
- Used and unused double-masked investigational product collected, counted, and compliance assessed (via subject diary)
- Subject-rated assessment of ocular discomfort
- Investigator-rated assessment of bulbar conjunctival hyperemia
- [REDACTED]
- BCVA
- Slit Lamp Biomicroscopy:
- Corneal fluorescein staining
- Lissamine Green conjunctival staining
- IOP measurement
- Dilated ophthalmoscopy
- UPT
- Release of subject from the study

#### 5.1.7. Unscheduled Visit

Any visits or procedures performed beyond those specified within the protocol must be documented in the Unscheduled Visit pages of the eCRF. Unscheduled visits may include but are not limited to reporting adverse events (AEs), changes in concomitant medications, or ophthalmic assessments as deemed appropriate by an appropriately qualified physician. If the subject is discontinuing study participation at the unscheduled visit, the eCRFs for Visit 6 should be completed rather than the eCRFs for an Unscheduled Visit.

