#### 5.1.8. Early Termination Visit

In the event of termination prior to Visit 6, every attempt will be made to ensure that all Visit 6 assessments are performed. If this is not feasible, at least the following should be performed/assessed:

- Use of any concomitant medications since the last visit
- Occurrence of any AEs since the last visit
- Used and unused investigational product collected and compliance [REDACTED]

- [REDACTED]
- BCVA
- Slit lamp biomicroscopy
- IOP measurement

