## 5.2. RESCUE MEDICATION USE

Any subjects not responding adequately to the study medication may be rescued and placed on alternate therapy at the Investigator's discretion at any time. The choice of rescue medication is at the Investigator's discretion. Any subject placed on rescue therapy will discontinue use of the study medication and continue study participation through Visit 6. Rescued subjects will be considered treatment failures, but the need for rescue therapy will not be considered an AE. Rescued subjects experiencing an AE at the time of rescue will be followed through stabilization or resolution of the AE or the end of the study (whichever comes last). Rescued subjects should not be withdrawn from the study, but rather followed to resolution of signs and symptoms or until the Investigator has deemed the subject is stable.

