## 5.3. SUBJECT WITHDRAWAL AND/OR DISCONTINUATION

Any subject who wishes to may withdraw from the investigational product use or from participation in the study of his or her own accord for any reason is entitled to do so without obligation. The Investigator may also withdraw any subject from the investigational product use or from study participation, if deemed necessary.

Investigational product use may be discontinued and any subject may be discontinued from study participation at any time during the study at the discretion of the Investigator or the sponsor for any reason including but not limited to:

1. Occurrence of any medical condition or circumstance that exposes the subject to substantial risk and/or does not allow the subject to adhere to the requirements of the protocol.
2. Any SAE, clinically significant AE, severe laboratory abnormality, intercurrent illness, or other medical condition that indicates to the Investigator that continued participation is not in the best interest of the subject.
3. Subject's decision to withdraw.
4. Any woman who becomes pregnant while participating in the study. Information on the pregnancy and outcome will be requested.
5. Subject's failure to comply with protocol requirements or study related procedures.
6. Termination of the study by the Sponsor, FDA, or other regulatory authorities.

In the event study discontinuation of a randomized subject is necessary, the Investigator should make every attempt to have subject complete Visit 6 assessments as possible. If a non-serious AE is unresolved at the time of the subject's final study visit, an effort will be made to follow up until the AE is resolved or stabilized, the subject is lost to follow-up, or there is some other resolution of the event. The Investigator should make every attempt to follow all serious adverse events (SAEs) to resolution. The reason for premature discontinuation should be entered onto the Case Report Form (CRF) and recorded in the subject chart.

Subjects who withdraw from the study will not be replaced.

Additionally, the trial or parts of the trial may be discontinued by the sponsor or at the recommendation of the Investigator after consultation with Kala Pharmaceuticals, Inc. This may be based on a significant number of AEs of a similar nature that warrant such action.

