#### 9.1.2. Analysis of Efficacy

The primary analysis population will be the Intent-to-Treat (ITT) population, defined as all subjects randomized. A subset of efficacy analyses will be examined for the Efficacy Evaluatable (EE) population, the definition of which will be outlined in the Statistical Analysis Plan and finalized prior to unmasking of study data pursuant to clinical data review.

The primary analysis of all ophthalmic efficacy measures will be based on the single study eye for each subject.

The co-primary endpoints are (1) the mean bulbar conjunctival hyperemia score at Visit 6; and (2) the mean [REDACTED] severity score averaged over the days from Visit 5 to the day before Visit 6.

Secondary and exploratory efficacy endpoints will be evaluated as elaborated in [Section 3](#).

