## **9.4. PROCEDURE FOR ACCOUNTING FOR MISSING, UNUSED, OR SPURIOUS DATA**

Any missing, unused, or spurious data will be noted in the final clinical study report. Multiple imputation will be employed to analyze incomplete data sets under the assumption that missing data are, at worst, characterized as missing at random (MAR). The reasons for missing data will be recorded and the impact of these reasons and any treatment group imbalance on the assumption of MAR will be evaluated. Imputation will be carried out only on the co-primary endpoints and time points.

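### Could a hyperemia score taken at early exit, but entered on the Visit 6 pages, pass as the Visit 6 co-primary value?

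*Combined protocol and SAP*

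**What the plan says.** Section 5.1.7 covers visits outside the schedule. It states: "If the subject is discontinuing study participation at the unscheduled visit, the eCRFs for Visit 6 should be completed", in place of the unscheduled-visit pages. Section 5.1.8 adds: "In the event of termination prior to Visit 6, every attempt will be made to ensure that all Visit 6 assessments are performed". Section 5.3 repeats the request for any randomized subject who discontinues. The Visit 6 list in 5.1.6 includes hyperemia. The readable fallback list in 5.1.8 does not, although one of its items is redacted.

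On timing, 5.1.6 states: "The end-of-investigational-product-use visit will occur on Day 29 ± 1 day as calculated from Visit 2: Day 1". Appendix 1 gives the same window.

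On analysis, 9.1.2 states: "The co-primary endpoints are (1) the mean bulbar conjunctival hyperemia score at Visit 6". Section 9.4 states: "Multiple imputation will be employed to analyze incomplete data sets", under a missing-at-random assumption and for the co-primary endpoints and time points only. Section 9.1.2 refers to a separate Statistical Analysis Plan, whose text is not in the document reviewed.

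Rescue is a different case. Under 5.2, "Any subject placed on rescue therapy will discontinue use of the study medication and continue study participation through Visit 6". The question therefore concerns only subjects who leave the study.

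**The concern.** Read together, 5.1.7 and 9.1.2 seem to let a score from, say, Day 10 sit in the Visit 6 field, look complete and never reach the imputation step. A subject leaving before Visit 5 would have no diary days in the window of the second co-primary. That score would be imputed while hyperemia counted as observed, so one dropout would be handled in two ways.

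Three things would be at stake:

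- **Dilution.** Scores after short exposure carry less of the drug effect.
- **Bias.** If exit rates differ by arm and exit scores are worse than Day 29 scores would have been, the between-arm difference shifts.
- **Reproducibility.** Two analysts could build different primary datasets from the same forms.

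**Working it through.** **1. The passages side by side.** Section 5.1.7 governs data entry. Section 5.1.6 and Appendix 1 define Visit 6 by study day counted from Visit 2. Section 5.1.8 describes termination as prior to Visit 6, so for such a subject Visit 6 has not occurred. A score from that occasion is then not a Visit 6 score under 9.1.2, and 9.4 applies. On this reading both co-primaries are imputed for a subject who leaves before Visit 5, and the inconsistency disappears. No passage directs analysis by page label.

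**2. Can the analyst tell the records apart?** Section 5.3 puts the reason for premature discontinuation on the case report form. Section 9.4 has reasons for missing data recorded and any arm imbalance weighed against the missing-at-random assumption. Study day follows from the visit date, which I assume is recorded on the page.

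**3. The plan's sample size.** Section 9.2 gives 71 per group and 90% power but redacts the effect size and significance level, so 71 cannot be reproduced independently. Taking two-sided 0.05 from 9.3 and solving the two-sample t-test backwards gives d = 0.548. The normal approximation gives (1.960 + 1.282) × √(2/71) = 0.544. With 150/2 = 75 per arm, power at d = 0.548 is 91.5%.

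**4. Dilution if analysed by label.** Let q be the share of the active arm leaving early with hyperemia measured, and f the share of the effect reached by then. The diluted effect is d × [1 − q(1 − f)]. The documents give no dropout rate. I take q = 0.053, from (150 − 142)/150, and q = 0.15; both are assumptions. Completers-only power at full d is a rough stand-in for imputation, with 75 × 0.85 = 63.75 per affected arm at q = 0.15.

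| q | f | Diluted d | By label | Completers, loss in both arms | Completers, loss in active arm only |
|---|---|---|---|---|---|
| 0.053 | 0.5 | 0.548 × 0.9735 = 0.533 | 90.1% | 90.0% | 90.8% |
| 0.053 | 0 | 0.548 × 0.947 = 0.519 | 88.4% | 90.0% | 90.8% |
| 0.15 | 0.5 | 0.548 × 0.925 = 0.507 | 86.9% | 86.6% | 89.1% |
| 0.15 | 0 | 0.548 × 0.85 = 0.466 | 80.9% | 86.6% | 89.1% |

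At half effect with loss in both arms, labelling costs nothing beyond what missing data cost anyway. The largest gap, 89.1 − 80.9 = 8.2 points, needs 15% loss in the active arm only, no effect at all by exit, and hyperemia measured in every leaver.

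**5. Bias if analysed by label, with no true effect.** The shift equals (vehicle exit rate − active exit rate) × excess of the exit score in SD. The noncentrality is shift/√(2/75), with 148 degrees of freedom. The nominal upper-tail error is 2.5%.

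| Vehicle / active exit | Excess (SD) | Shift (SD) | Error favouring active |
|---|---|---|---|
| 15% / 5% | 0.5 | 0.05 | 4.9% |
| 15% / 5% | 0.25 | 0.025 | 3.5% |
| 8% / 4% | 0.5 | 0.02 | 3.3% |
| 6% / 4% | 0.5 | 0.01 | 2.9% |
| 5% / 15% | 0.5 | −0.05 | 1.2% |

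These rates are for hyperemia alone. Section 9.3 requires the second co-primary as well.

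**6. Does treating exit scores as missing do better?** Simulated null trials with 15% / 5% exit and 0.5 SD, imputing from baseline and arm, give:

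- *Exit score worse, Day 29 score unaffected:* by label 5.0% to 5.2%, imputation 2.6%.
- *Leavers truly worse at Day 29 by about the same amount:* by label 2.1% to 3.0%, imputation 1.1% to 1.4%.

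In the second case imputation makes leavers resemble completers. That flatters the vehicle arm by (0.15 − 0.05) × 0.5 = 0.05 SD, and the formula in step 5 gives 1.2% for that shift, in line with the simulation. Which case holds cannot be learned from the documents.

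**The case for a change.** The strongest counter-argument is that Day 29 ± 1 is a visit schedule and not an analysis window, and that 5.1.7 expressly sends data to the Visit 6 pages off that schedule. The protocol itself states the endpoint and the missing-data method, so it could reasonably state this too. Both co-primaries must succeed, and under some inputs labelling about doubles the one-sided error on one of them. A clarifying sentence would be cheap.

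Part of this stands. The supplied text has no explicit mapping rule, a programmer working from page labels alone could go wrong, and the power and error figures reproduce.

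The rest does not lead to a change. Visit windows and the assignment of off-schedule records are ordinary content of the separate analysis plan, and their absence here does not show that they are absent there. The fuller remedy would be to declare exit scores missing and use them as predictors in the imputation. A visit-based model cannot estimate that relation, because exit scores exist only in subjects with no Visit 6 score. A model in continuous time would be needed for a handful of subjects.

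**Conclusion.** The concern does not call for a change. It is a gap in detail that analysts fill sensibly: the visit definitions already place an early exit before Visit 6, the subjects concerned can be identified, and the passage that prompted the worry concerns form completion.

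With about 5% early exit, the difference in power between the two treatments of the data runs from nil to about 2 points (90.8 − 88.4 = 2.4 at most). The larger figures, 8 points of power or a one-sided error of 4.9%, need 15% exit in one arm together with unfavourable early scores. Whether label or imputation lies nearer the nominal error depends on what leavers would have scored at Day 29. All of this rests on d = 0.548 at two-sided 0.05, 75 per arm, and assumed exit rates and exit scores. It applies only to subjects who leave the study and have hyperemia measured when they do.
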